4.7. Procedures for Monitoring Subject Compliance

All IMPs will be injected by the investigator or other clinical personnel at the investigational center; therefore, monitoring of subject compliance will not be necessary.

4.8. Total Blood Volume

The total volume of blood to be collected for each subject in this study is approximately 345 mL as detailed in [Table 4](#).

Table 4: Approximate Blood Volumes

Assessments	Volume per sample (mL)	Total number of samples	Total volume (mL)
Pharmacokinetics	MPA: about 5 mL	32	160 mL
Clinical laboratory	Hemoglobin: about 5 mL Liver enzymes: about 5 mL P: about 5 mL E2: about 5 mL	Hemoglobin: 1 Liver enzymes: 5 P: 6 E2: 25	Hemoglobin: 5 mL Liver enzymes: 25 mL P: 30 mL E2: 125 mL
Approximate Total		69	345 mL

MPA: Medroxyprogesterone acetate

4.9. Withdrawal of Subjects

4.9.1. Subject Withdrawal Criteria and Procedures

In accordance with the Declaration of Helsinki, each subject is free to withdraw from the study at any time. The investigator also has the right to withdraw a subject from the study in the event of intercurrent illness, adverse events, pregnancy (see Section 5.1) or other reasons concerning the health or well-being of the subject, or in the event of lack of cooperation.

Should a subject decide to withdraw from the study, or should the investigator decide to withdraw the subject, every reasonable effort will be made to assess information relevant to the endpoints at the time of discontinuation. This may include but may not be limited to MPA testing, pregnancy testing, assessment of ISRs and/or acceptability. The final visit procedures will be followed for all subjects who withdraw, if possible (see Section 3.4).

The reason for and date of withdrawal from the study must be recorded on the source documentation and transcribed onto the CRF. If a subject withdraws consent, every attempt will be made to determine the reason.

If the investigator determines that an adverse event is related to the test IMP, monitoring will continue until the adverse event has resolved or stabilized, the subject exited the study or the subject has reached the end of the follow-up period. The investigator must inform FHI 360 as soon as possible of all subjects who are being considered for withdrawal due to adverse events. Additional reports must be provided when requested.

The study product remains in the body months after the injection, therefore, prompt withdrawal from the study treatment is not possible, and discontinuation from the study will not be the same as withdrawal from treatment. Study staff will explain to subjects who wish to discontinue from the study early that it is impossible to discontinue the treatment and that it is important to stay in the study until safety assessments are completed.

4.9.2. Lost to Follow-up

If a subject fails to appear for a scheduled visit, at least 3 attempts to contact the subject will be made. If she does not return to clinic while the study is ongoing then she will be considered “presumed lost to follow-up”, but her file will remain open until study closeout. If the subject

does not return before the study is closed, she will be classified as lost to follow-up. The lost to follow-up designation will not be made for any subject until the closing date of the study.

5. SAFETY MEASUREMENTS AND ASSESSMENTS

5.1. Safety and Tolerability Measurements

The following safety and local tolerability measures will be implemented throughout the study at the time points listed in [Table 1](#):

- occurrence of adverse events
- use of concomitant medication
- vital signs and body weight measurements
- vaginal bleeding pattern
- assessment of mood by Patient Health Questionnaire-9 (PHQ-9)
- liver function tests
- E2 levels throughout the study
- P measurements at Weeks 48, 49, 50, 51, and 52
- occurrence of ISRs

5.1.1. Adverse Events

Information on adverse events will be monitored throughout the study as detailed in [Table 1](#).

During scheduled follow-up visits, study staff will proactively ask study subjects about any new or worsening medical issues since the previous visit. At all other visits information on adverse events will be recorded if self-reported by study subjects.

See Section [5.2](#) for details on adverse event recording and reporting.

5.1.2. Concomitant Medication Use

Concomitant therapy or medication usage will be monitored throughout the study as detailed in [Table 1](#).

During scheduled follow-up visits, study staff will proactively ask study subjects about any new medication since the previous visit. At all other visits information on concomitant medication use will be recorded if self-reported by study subjects. Details of prohibited medications are found in Section [4.6](#).

5.1.3. Vital Signs and Body Weight Measurement

Vital signs (BP [systolic/diastolic], temperature, pulse and respiration rate) and weight will be measured as detailed in [Table 1](#).

Before pulse and BP are measured, the subject must be in a supine or semi-erect/seated position and resting for at least 5 minutes. The same position and arm should be used each time vital signs are measured for a given subject. Any vital sign value that is judged by the investigator as a

potentially clinically significant change (worsening) from Day 0 will be considered an adverse event.

Weight gain or loss will be documented as an adverse event if considered clinically significant by the site investigator.

5.1.4. Assessment of Vaginal Bleeding

Study subjects will be asked about their vaginal bleeding pattern since last assessment during the scheduled follow-up visits at Weeks 13, 26, and 52. Interview items will include date of last bleeding, description of bleeding pattern since last visit, and its acceptability.

5.1.5. Assessment of Mood

Subjects will be interviewed about aspects of and changes in mood at enrollment and at pre-defined timepoints throughout the study ([Table 1](#)). To measure depression or psychological distress, a selected validated scale based on the 10-item PHQ-9 ([Kroenke et al 2001](#)) will be used to ascertain the frequency of a variety of somatic and emotional indicators of well-being and produce an overall score for the severity of depression that will be compared between Day 0 and different time points in the study.

5.1.6. Liver Function Tests

Liver function testing will be performed by the investigational center laboratory as detailed in [Table 1](#).

The following tests will be included in the liver panel:

- Alkaline phosphatase (ALP)
- Aspartate aminotransferase (AST)
- Alanine aminotransferase (ALT)
- Total protein
- Albumin
- Total and direct bilirubin

All occurrences of possible drug induced liver injury that meet Hy's law criteria, defined as all of the below, must be reported by the investigator to the sponsor as a serious adverse event:

- ALT or AST increase of >3x the upper limit of normal (ULN)
- total bilirubin increase of >2x ULN
- absence of initial findings of cholestasis (ie, no substantial increase of ALP)

5.1.7. Estradiol Measurement

All enrolled subjects will provide blood for E2 measurement before the injection to document the baseline level. During the study, all subjects will return for serum E2 testing according to the pre-defined schedule ([Table 1](#)).

5.1.8. Assessment of Return to Ovulation at 52 Weeks

All enrolled subjects will provide blood for P measurement before the injection. During the study, all subjects will return for serum P testing according to the pre-defined schedule ([Table 1](#)).

During the treatment phase of the study, if P is ≥ 4.7 ng/mL in a single sample ovulation will be considered confirmed for the purpose of the analysis.

5.1.9. Injection Site Reactions

Injection site reaction (ISR) will be evaluated as detailed in [Table 1](#).

Local tolerability will be assessed by occurrence of ISRs including but not limited to erythema (redness), swelling, pruritus (itching), bleeding, bruising, injection site discoloration (eg, hypopigmentation), atrophy (ie, dimple) or injection site pain. For the purpose of this protocol, injection site pain will include pain associated with injection and any pain or tenderness at/around the injection site.

The site of injection will be evaluated for possible ISRs after the injection at least twice during the injection visit immediately (ie, as soon as possible but no later than 10 minutes upon removing the needle) and 1 hour (± 5 minutes) after the injection. Injection sites will be monitored for the progress of ongoing and/or occurrence of new ISRs. If the subject has new or ongoing ISR at Week 52, she will be followed every 3 months (at Weeks 65 and 78) until ISR resolution or Week 78, whichever is earlier. All ongoing ISRs will be examined during the next clinic visit, regardless of visit type, or more frequently at the discretion of the investigator, until ISR resolution, or the final visit, whichever occurs first.

ISRs will be evaluated at all study timepoints listed in [Table 1](#) by subject's self-reports and visual examination of the site of injection by blinded study staff. The study staff will be instructed to use non-leading questions (eg, "Do you have any new medical issues since previous visit?") for ISR ascertainment. If the subject reports injection site pain at any time during the study, she will be asked to assess the pain using an 11-point Numeric Rating Scale (NRS) by indicating a number between 0 (no pain) and 10 (worst pain).

All findings will be recorded on the appropriate study CRFs and clinical notes. Photos of the injection site may be taken to supplement documentation of ISRs any time during the study. All cases of injection site discoloration (hypopigmentation) will be photographed. If necessary, a consultation with an appropriate clinical expert may be scheduled.

The following ISRs will be documented as adverse events:

- Injection site pain with an NRS score of 7 to 10
- Injection site pruritus/itching if itching localized to the injection site requiring ≥ 48 hours of treatment OR generalized itching causing inability to perform usual social and functional activities
- Injection site erythema/redness of ≥ 5 cm in diameter (or ≥ 25 cm² surface area) or greater than minimal interference with usual social and functional activities
- Injection site induration/swelling of ≥ 5 cm in diameter (or ≥ 25 cm² surface area) or greater than minimal interference with usual social and functional activities

- Any ISR that meets the definition of “serious adverse event”

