4.4. Stopping Rules and Discontinuation Criteria

If, at any time one of the following occurs: two or more ISRs graded as severe adverse events, 15 cases of skin discoloration at injection site (eg, hypopigmentation) ongoing for more than 7 days, or two serious and related adverse events in the study across all treatment groups, an unplanned review of interim data by a Study Review Committee (SRC), will occur, at which time a recommendation may be made to pause enrollment or halt the study. Other planned reviews will take place as scheduled (see Section 9.8), at which time the SRC could advise that the study stop or be modified based on concerns for safety of subjects or definitive conclusions.

Since most of the study drugs are expected to remain in the body months after injection, study discontinuation will not be the same as treatment discontinuation. Study staff will explain to subjects who wish to discontinue the study early that it is important to stay in the study until safety assessments are completed. However, a subject may discontinue participation in the study at any time for any reason (eg, withdrawal of consent or an adverse event) without loss of other benefits or services to which they may be entitled. All subjects who discontinue early will be followed according to Subject Withdrawal Criteria and Procedures (Section 4.9.1). Reasons for discontinuation from the study will be recorded on the appropriate electronic case report form (eCRF).

Others reasons the study may be stopped include:

- Institutional Review Board (IRB)/ Independent Ethics Committee (IEC) recommend terminating the study
- The Food and Drug Administration (FDA) requests that the study be discontinued or placed on hold.
- The sponsor decides to reduce the scope (eg, reduce sample size, drop one or more study groups) or terminate the study. The sponsor may terminate the study at any time for any reason.

If the whole study is stopped, the subjects that are terminated early will be followed according to Subject Withdrawal Criteria and Procedures (Section [4.9.1](#)).

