5.2.3. Severity of an Adverse Event

The severity of each adverse event must be recorded as 1 of the choices on the following scale:

Mild:	No limitation of usual activities
Moderate:	Some limitation of usual activities
Severe:	Inability to carry out usual activities

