8.4. Injection Site Reactions

A summary table of ISRs will include numbers of events, and numbers and percentages of subjects, experiencing a) any ISR; b) ISRs documented as adverse events on CRF data (per protocol criteria); and c) hypopigmentation events. Exact Cochran-Armitage tests of trend will be used to explore relationships between MPA dose and the probability of experiencing ISRs.

ISRs will be further tabulated according to specific categories, including but not necessarily limited to erythema, swelling, pruritus, bleeding, bruising, hypopigmentation, atrophy, and injection site pain. The maximum recorded size of ISRs (if applicable) will be summarized using descriptive statistics for continuous variables. An 11-point numeric rating scale will be used to describe reports of injection site pain. Listings of ISRs will include time to onset, duration,

Statistical Analysis Plan Version 5.0

Pharmacokinetics Study–Healthy Subjects

Study TV46046-WH-10159

outcome, and whether the ISR was self-reported by the subject or noted by clinic staff when performing an assessment of the injection site.

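### Non-serious injection-site pain scored 6 or less that stops usual activities fits the protocol's definition of severe, but it is not on the list of reactions documented as adverse events and so does not count toward the severe-reaction review trigger

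*Protocol*

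**What the plan says.** Protocol 5.1.9 introduces its list with "The following ISRs will be documented as adverse events". The routes onto it differ by type of reaction:

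- Pain: "Injection site pain with an NRS score of 7 to 10", with no other route.
- Itching: localized itching that needs at least 48 hours of treatment, or "generalized itching causing inability to perform usual social and functional activities". The functional wording belongs to generalized itching only.
- Erythema and swelling: a size threshold, "or greater than minimal interference with usual social and functional activities".
- Any ISR that meets the definition of a serious adverse event (SAE).

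The same section has every finding entered on the CRF and an NRS score taken whenever pain is reported.

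Protocol 5.2.3 has one severity scale for all AEs, based on limitation of activity. Severe means "Inability to carry out usual activities".

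Protocol 4.4 calls an unplanned Study Review Committee (SRC) review if, among other things, there are "two or more ISRs graded as severe adverse events", pooled across groups.

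SAP 8.3 tabulates treatment-emergent AEs, including by severity. SAP 8.4 summarizes (a) any ISR, (b) "ISRs documented as adverse events on CRF data (per protocol criteria") and (c) hypopigmentation. It also tabulates ISRs by category and describes pain on the 11-point scale.

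**The concern.** Two different yardsticks are applied in sequence. Whether pain becomes an AE depends on its intensity score. Whether an AE is severe depends on function. Pain that fails the first test never reaches the second, however disabling it is. Erythema or swelling with the same effect on daily life does reach it, because those bullets have a functional alternative.

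At stake is the pre-specified early warning for local harm. Local tolerability is a secondary objective. In the earlier study (Protocol 1.2.2.2), ISRs were the most frequent AE, in 9 of 12 women, and appeared more common than in historical data on approved products. The injected drug stays in the body for months and treatment cannot be withdrawn (Protocol 4.9.1). The trigger needs only two events among about 60 women, so one uncounted event can decide whether it is met.

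**Working it through.** **Step 1: follow one event through the text.** Take non-serious injection-site pain with an NRS score of 5 or 6 that leaves a woman unable to do her usual activities.

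| Place | Test applied | Result |
|---|---|---|
| Protocol 5.1.9, recording | Is it a finding? | Yes: on the CRF, with its NRS score |
| Protocol 5.1.9, AE list | NRS 7 to 10, or serious? | No: not listed as an AE |
| Protocol 5.2.3 | Severity grade of an AE | None assigned; the description matches severe |
| Protocol 4.4 | ISR graded as a severe AE? | Not counted |
| SAP 8.3 | Treatment-emergent AEs | Absent |
| SAP 8.4 (a) and category tables | Any ISR; pain | Present, but activity limitation is not among the items named |
| SAP 8.4 (b) | ISR documented as an AE | Absent |

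Non-serious localized itching that prevents usual activities but needs less than 48 hours of treatment follows the same path. Erythema below the size threshold with the same functional effect does not: it enters through "greater than minimal interference with usual social and functional activities", is graded severe and counts.

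**Step 2: is the list really the filter?** Its lead-in does not say that only these ISRs qualify. But if every ISR were already an AE under the general definition in Protocol 5.2.1, the thresholds in 5.1.9 would have no effect. SAP 8.4 (b) also refers to protocol criteria as the thing that separates AE-documented ISRs from the rest. The filter reading is therefore the operative one. If sites could read it either way, AE counts and the trigger would depend on the site, which calls for the same repair.

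**Step 3: illustration of size.** The plan has no figure here to reproduce. Let *p* be the risk per woman of a functionally severe ISR and *f* the share of those not counted because they fall in the gap. Both are assumptions. Only *n* = 60 comes from the protocol. With *q* = *p*(1 − *f*):

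P(at least 2) = 1 − (1 − *q*)^60 − 60*q*(1 − *q*)^59

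- *p* = 5%, *f* = 0: *q* = 0.05, so 1 − 0.046 − 0.145 = 0.808 (unrounded terms)
- *p* = 5%, *f* = 50%: *q* = 0.025, so 1 − 0.219 − 0.337 = 0.444

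| *p* | *f* = 0 | *f* = 25% | *f* = 50% |
|---|---|---|---|
| 2% | 0.338 | 0.227 | 0.121 |
| 3% | 0.541 | 0.392 | 0.227 |
| 5% | 0.808 | 0.663 | 0.444 |
| 10% | 0.986 | 0.945 | 0.808 |

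The smallest loss is 0.986 − 0.945 = 0.041 and the largest is 0.808 − 0.444 = 0.364, or about 4 to 36 percentage points.

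**The case against.** The strongest reply is that little is lost, and several parts of it stand.

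- **A reader might infer that this pain goes unrecorded.** It does not. The pain and its score go on the CRF and appear in SAP 8.4 under any ISR and by category. What is missing is the AE label and the severity grade.
- **A reader might infer that pain scored 6 or less can never count.** That is too absolute. Any ISR meeting the SAE definition is an AE at any score, and that definition includes substantial disruption of normal functioning. The general AE definition in Protocol 5.2.1 is also not expressly switched off for such pain, whereas irregular bleeding is expressly carved out there. Still, severe is not the same as serious: a day or two without usual activities can be severe in 5.2.3 without being lasting or significant disability.
- **The trigger is not the only safeguard.** Protocol 4.5 says that ISRs may prompt an unplanned review, and SAP 2.6.1 leaves room for SRC discretion. This softens the consequence. It does not make the pre-specified count complete.
- **A reader might infer that grading NRS 10 pain as mild when it limits nothing is an error.** It follows from a functional scale. Intensity and functional effect are different things, and the NRS is reported separately.
- **The arithmetic is weak as evidence of effect size.** No document supports the assumed rates or score split, the earlier study describes most ISRs as mild and transient, and the model counts women while 4.4 counts ISRs. This is accepted, so the table is illustration only.

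**Conclusion.** The gap is real but narrow. It covers non-serious pain scored 6 or less, and localized itching needing less than 48 hours of treatment, when either prevents usual activities. Such an event is captured as an ISR. If the 5.1.9 list is the operative filter, as SAP 8.4 (b) indicates, the event is ungraded, absent from the AE tables and not counted in 4.4, although it matches the protocol's own wording for severe. Its frequency cannot be determined from the documents. The calculation shows only that a two-event trigger in about 60 women is sensitive to leaving out a moderate share of qualifying events. This is worth correcting because the repair is cheap and bears on safety monitoring. It does not show that the trigger fails or that data are lost.

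**What to change.** Reconcile Protocol 4.4, 5.1.9 and 5.2.3 so that any ISR meeting the functional definition of severe in 5.2.3 is documented as an AE and counted. One way is to give the pain and localized-itching bullets in 5.1.9 a functional route like the one for erythema and swelling. The exact threshold should be left to the sponsor. Reusing the erythema and swelling wording would also bring in reactions short of severe, whereas a clause tied to inability would close only the gap described here. A sentence should also say whether the 5.1.9 list is exhaustive. SAP 8.4 (b) needs no change, since it follows the protocol criteria.

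The cost is a clause in two bullets, a clarifying sentence, a few more ISRs documented as AEs, and asking about activity limitation when pain or itching is reported. No extra visits or samples are needed.

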5.1.10. Physical Examinations

Physical examination will be performed at screening to define inclusion/exclusion.

5.2. Safety Assessments

5.2.1. Definition of an Adverse Event

An adverse event is any untoward medical occurrence in a subject administered a pharmaceutical product, regardless of whether it has a causal relationship with the treatment.

In this study, any adverse event occurring after the clinical study subject has signed the ICF through the end of the follow-up period should be recorded and reported as an adverse event. An adverse event occurring during or after study injection is referred to as a treatment emergent adverse event

A new condition or the worsening of a pre-existing condition will be considered an adverse event. Stable chronic conditions (such as arthritis) that are present before study entry and do not worsen during this study will not be considered adverse events.

Accordingly, an adverse event can include any of the following:

- intercurrent illnesses
- physical injuries
- events possibly related to concomitant medication
- significant worsening (change in nature, severity, or frequency) of pre-existing conditions (Note: A condition recorded as pre-existing that is intermittently symptomatic [eg, headache] and that occurs during this study should be recorded as an adverse event.)
- drug interactions
- events occurring during diagnostic procedures
- laboratory or diagnostic test abnormalities, that result in the withdrawal of the subject from the study, are associated with clinical signs and symptoms or a serious adverse event, or require medical treatment or further diagnostic work-up, or are considered by the investigator to be clinically significant (Note: Abnormal laboratory test results at the screening visit that preclude a subject from entering the study or receiving study treatment are not considered adverse events.)
- all events of possible drug induced liver injury (Section [5.1.6](#))
- any physical examination, vital signs measurement, electrocardiogram, or other safety assessment finding that is judged by the investigator as a clinically significant change (worsening) compared with a baseline value will be considered an adverse event

- For the purpose of this study, irregular vaginal bleeding will not be considered an adverse event unless it requires medical intervention or meets the definition of “serious adverse event” (See Section 5.2.5).

